### **3.2.2 Per-Protocol Population**

The Per-Protocol (PP) Population is defined as all subjects enrolled in Phase 2 of the study, including the 6 subjects treated in Phase 1 at the MTD, who received at least 75% of the scheduled doses of MEDI4736 and PLD over the first 2 cycles, as well as respective disease assessments, without major protocol violations.

**Phase 2:** The Per-Protocol (PP) Population for Phase 2 is defined as all subjects enrolled in Phase 2 of the study who received at least 75% of the scheduled doses of MEDI4736 and PLD over the first 2 cycles, as well as respective disease assessments, without major protocol violations.

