## **3.3 Analysis Variables**

### **3.3.1 Clinical Efficacy**

Tumor response will be assessed using RECIST v1.1 and irRECIST criteria. When a radiological assessment is unavailable to determine RECIST (irRECIST), a clinical assessment of progressive disease and/or death may be used in lieu of the RECIST (irRECIST) to determine disease response. This combined clinical efficacy endpoint will be used in the primary efficacy analysis. RECIST and irRECIST criteria are described in detail in the protocol, and an abbreviated description is provided below.

RECIST evaluation of target lesions are as follows:

Response	Criteria for Response
Complete Response (CR)	Disappearance of all target lesions
Partial Response (PR)	At least a 30% decrease in the sum of the diameters of target lesions taking as reference the baseline sum diameters
Stable Disease (SD)	Neither sufficient shrinkage to qualify for PR nor sufficient increase to qualify for PD
Progressive Disease (PD)	At least 20% increase in the sum of the diameters of target lesions taking as reference the baseline sum diameters or new lesion identification

irRECIST evaluation of target and new lesions are as follows:

Complete Response (irCR)	Complete disappearance of all target and new, measurable lesions, with the exceptions of lymph nodes which must decrease to < 10 mm in short axis.
Partial Response (irPR)	Decrease in TMTB* $\geq$ 30% relative to baseline.
Stable Disease (irSD)	Not meeting criteria for irCR or irPR, in absence of irPD.
Progressive Disease (irPD)	Increase in TMTB $\geq$ 20% relative to nadir.

\*TMTB = SumD target lesions + SumD new, measurable lesions.

For both RECIST and irRECIST, if CA125 levels are initially above the upper normal limit, they must normalize for a subject to be considered in complete clinical response.

Efficacy variables include:

- Progression-free Survival
  - Proportion of subjects surviving without progression at 6 months (based on RECIST v1.1 and/or clinical progression/death) – Phase 2 primary endpoint
  - Proportion of subjects surviving without progression at 6 months (based on irRECIST and/or clinical progression/death) – Phase 2 secondary endpoint
  - Proportion of subjects surviving without progression at 12 months (based on RECIST v1.1 and irRECIST and/or clinical progression/death) – Phase 2 secondary endpoints

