### **3.8 Efficacy Analysis**

#### **3.8.1 Progression-free Survival**

The primary endpoint in Phase 2 of this study is the PFS rate at 6 months defined as the visit at the start of Cycle 7, where progression is assessed for subjects based on a combination of RECIST v1.1 and/or the clinician's assessment of clinical progression or death. The primary efficacy analysis will be based on the Per Protocol population. A sensitivity analysis will be conducted on the ITT population. A secondary efficacy analysis will be conducted on the Phase 2 Per Protocol population.

The primary efficacy analysis entails testing the null hypothesis that PFS at 6 months is less than or equal to 25% against the alternative hypothesis that PFS at 6 months is higher for those treated with PLD and MEDI4736 combination. This hypothesis will be tested at  $\alpha=0.05$  using the 90% two-sided confidence interval for the PFS rate at 6 months based on Kaplan-Meier product limit estimates. The null hypothesis will be rejected in favor of the alternative if the lower bound of that confidence interval is greater than 25%. The null hypothesis will also be tested using a one-sided binomial test as a sensitivity analysis. In this analysis, if a subject has no tumor response assessment, or discontinued treatment or withdrew from the study for other reasons, he or she will be considered as "progressed." The null hypothesis will be rejected in favor of the alternative if the lower bound of a two-sided 90% binominal confidence interval is greater than 25%.

Table displays will include PFS rate at 6 months and the corresponding 90% confidence interval along with the corresponding number of subjects at risk. In addition, PFS will be presented graphically.

Secondary efficacy analyses will use the secondary efficacy endpoints listed in section 3.3.1 of the SAP and will be based on the ITT population. PFS rate and the corresponding 95% confidence interval will be calculated based on Kaplan-Meier product limit estimates and will be displayed by cohort and phase.

Descriptive analyses of PFS will include the following:

- Number and percentage of subjects that died or had a confirmed progression,
- Number and percentage of subjects that survived without a confirmed progression,
- Number and percentage of subjects lost to follow up (unknown survival and/or progression status), and
- Number of subjects missing the tumor response assessment

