PFS time will be summarized for each cohort and phase and will include the 25th percentile, median, 75th percentile, corresponding 95% CIs, minimum and maximum, where PFS time will be calculated using the Kaplan-Meier method. In addition, PFS will be presented graphically.

PFS time is defined as time from the start date of the treatment (Day 1) to the first occurrence of confirmed progression (clinical or radiological), or the date of death due to any cause, whichever occurs first. Subjects without documentation of progression at the time of the analysis will be censored at the date of the last tumor response assessment, date of start of alternate therapy, or last contact if in post study follow-up, whichever comes first. Subjects with no tumor response assessment will be censored at the start date of the treatment.

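### SAP 3.8.1 does not say whether a death or clinical progression before the first scan is a PFS event or is censored at Day 1

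*SAP*

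**What the plan says.** SAP 3.8.1 measures PFS time from Day 1 "to the first occurrence of confirmed progression (clinical or radiological), or the date of death due to any cause, whichever occurs first". No scan is needed for an event. Two censoring sentences follow in the same paragraph:

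- "Subjects without documentation of progression at the time of the analysis will be censored at the date of the last tumor response assessment", or at the start of alternate therapy or at last contact in post-study follow-up, if that is earlier.
- "Subjects with no tumor response assessment will be censored at the start date of the treatment".

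The first does not exempt a subject who died without documented progression. The second exempts neither death nor clinical progression. Nothing states which rule takes precedence.

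Other SAP text bears on the same subjects:

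- SAP 3.3.1: when radiology is unavailable, "a clinical assessment of progressive disease and/or death may be used in lieu of the RECIST (irRECIST) to determine disease response". It adds: "This combined clinical efficacy endpoint will be used in the primary efficacy analysis".
- SAP 3.8.1, primary endpoint: progression rests on RECIST v1.1 and/or the clinician's judgement of clinical progression, or death.
- SAP 3.8.1, binomial sensitivity analysis: the subject counts as progressed "if a subject has no tumor response assessment, or discontinued treatment or withdrew from the study for other reasons".

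The primary analysis uses the per-protocol (PP) population, with ITT as a sensitivity analysis; the secondary PFS analyses use ITT. SAP 3.2.2 requires at least 75% of the MEDI4736 and PLD doses over the first two cycles, "as well as respective disease assessments, without major protocol violations".

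Both flowcharts (Protocol 3.2, repeated in SAP Table 1) put the first on-treatment disease assessment at Cycle 4 Day 1, target Day 85. The next is Cycle 7 Day 1, Day 169, which defines the 6-month time point.

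**The concern.** Take a subject who dies on Day 60 with no extra scan. The event definition makes her a failure on Day 60. The last censoring sentence, read alone, censors her at Day 1. Two programmers could both follow the text and produce different curves.

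The difference is not neutral. A subject censored at Day 1 contributes nothing to the estimate at Day 169, so the effect is the same as deleting her. Those deleted would be the earliest failures, so the estimated PFS rate can only rise. The ITT analysis, which should show what PP selection leaves out, would use the same censoring rule and could drop the same failures. The 12-month rate, median PFS and the irRECIST versions inherit the problem. The first censoring sentence adds a milder form of it: a death after a clean scan, without documented progression, could be censored at that scan.

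**Working it through.** **1. The plan's own figure.** Protocol 3.1.6 gives n = 41, null 25%, alternative 45%, one-sided alpha 0.05, exact test, 80% power. The smallest r with P(X ≥ r | 41, 0.25) ≤ 0.05 is 16:

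- P(X ≥ 15 | 0.25) = 0.0666
- P(X ≥ 16 | 0.25) = 0.0333
- P(X ≥ 16 | 0.45) = 0.8225

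The stated 80% is met. With full follow-up, the Kaplan-Meier rule in SAP 3.8.1 also needs 16 of 41 under a linear or log-log interval.

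**2. Status of an unscanned subject with an event before Day 85.**

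| Rule | Status |
|---|---|
| PFS event definition, SAP 3.8.1 | failure on the event date |
| No-scan substitution, SAP 3.3.1 | may count as failure |
| Binomial sensitivity rule, SAP 3.8.1 | failure |
| Day 1 censoring sentence, read literally | censored, no risk time |

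There are two outcomes, failure or censored, and no tie-break.

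**3. Effect on the decision.** Assume every other subject is followed to Day 169 or to an event. Then the Kaplan-Meier estimate is S = x/n, Greenwood gives SE = √(S(1−S)/n), and the linear lower limit of the two-sided 90% interval is S − 1.645·SE. The null is rejected if this exceeds 25%. All counts are assumed.

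- Two unscanned early failures counted as events: S = 15/41 = 0.3659; SE = 0.0752; lower = 0.3659 − 1.645 × 0.0752 = 0.242.
- The same two censored at Day 1: S = 15/39 = 0.3846; SE = 0.0779; lower = 0.3846 − 1.645 × 0.0779 = 0.256.

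The SAP names no interval transformation, so three were tried. The 16/45 and 16/40 rows assume 45 treated (ITT) and five such subjects.

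| x/n | S | Linear | Log-log | Clopper-Pearson | Reject? |
|---|---|---|---|---|---|
| 15/41 | 36.6% | 24.2% | 24.5% | 24.1% | no |
| 15/39 | 38.5% | 25.6% | 25.8% | 25.4% | yes |
| 16/45 | 35.6% | 23.8% | 24.1% | 23.7% | no |
| 16/40 | 40.0% | 27.3% | 27.3% | 26.9% | yes |

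**4. Effect on the error rate.** Let e be the share of the 41 subjects who fail early and unscanned and are all censored at Day 1. The estimated rate becomes p/(1−e). Type I error at p = 0.25 is found by summing over the number censored, binomial(41, e), and then over the number progression-free among the rest.

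| e (assumed) | Rate estimated | Type I, linear | Type I, log-log |
|---|---|---|---|
| 0% | 25.0% | 0.0333 | 0.0333 |
| 5% | 26.3% | 0.0525 | 0.0628 |
| 10% | 27.8% | 0.0808 | 0.0841 |
| 15% | 29.4% | 0.1196 | 0.1203 |
| 20% | 31.3% | 0.1717 | 0.1718 |

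If these subjects are counted as events, type I error stays at 0.0333 whatever e is.

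**5. Reach into the primary analysis.** On the Q4W schedule the Cycle 1–2 doses fall on Days 1, 3, 29 and 31, so the PP dosing condition can be met by Day 31, 54 days before the first scheduled scan. No post-baseline scan is due in Cycles 1–2 (Days 1–56). If the baseline scan satisfies the PP disease-assessment condition, a fully dosed subject who dies between Days 31 and 85 is in PP and the conflict reaches the primary test. If a post-baseline scan is required, she is outside PP and only the ITT analyses are affected.

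**The case against.** The strongest reply is that the SAP already means to count these subjects. SAP 3.3.1 addresses the missing-scan case and ties it to the primary analysis. SAP 3.8.1 repeats the combined endpoint, and its event definition needs no scan. Read in order, the Day 1 sentence then covers only subjects left without an event who also have no scan. That is probably the intent. It does not settle the matter, because the substitution in 3.3.1 is permissive and precedence is never stated.

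Three further points stand and limit the concern:

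- Stopping treatment early does not by itself leave a subject unscanned. The flowchart schedules an On Study Follow-up scan 84 ± 7 days after the last assessment. Counted from a baseline scan on Day −14 to −1, the target is roughly Day 70 to 84. Those at risk of having no scan are subjects who die, withdraw, are lost or start other therapy first.
- The binomial sensitivity analysis counts unscanned subjects as failures, so a large discrepancy would show.
- The worked counts sit near the cutoff by choice.

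A reader might infer that SAP 3.8.1 simply discards early deaths and clinical progressions, or that it gives one subject three different statuses. The documents support neither. Their other rules point to counting these subjects, and an event and a binomial failure are the same status.

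**Conclusion.** The point holds as a conflict between rules. Programmed literally, the censoring sentences are anti-conservative: PFS is biased upward in the ITT sensitivity and secondary analyses, and in the primary analysis only if the PP definition is met without a post-baseline scan. Two such subjects are enough to change the decision at 15 progression-free of 41 (lower bound 24.2% against 25.6%). Under the literal reading, type I error already passes 5% when 5% of subjects are affected. These sizes assume the counts and shares shown and no other censoring before Day 169. The documents give no expected number of early unscanned failures, so the figures show what could happen near the cutoff and do not forecast it. On the intended reading nothing changes, which is a reason to write that reading down.

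**What to change.** In SAP 3.8.1:

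1. State that a PFS event takes precedence over any censoring rule.
2. Limit Day 1 censoring to subjects with no post-baseline tumour assessment and no death or clinical progression.
3. State that death or clinical progression before the first scan is an event on its own date.
4. Reword the preceding sentence so that it applies to subjects with neither progression nor death.

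In SAP 3.2.2, say whether the disease-assessment condition requires a post-baseline scan, so that the reach into the primary analysis is known.

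The cost is a few lines of text. If the sponsor already intends this reading, no result changes. If not, the estimated PFS rate may be slightly less favourable.

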### **3.8.2 Tumor Response**

Tumor response will be summarized and analyzed descriptively for the ITT population.

The number and percentage of subjects meeting criteria of CR, PR, SD, and PD will be displayed. The number and percentage of subjects meeting criteria of CR or PR over a period of at least 4 weeks (Overall Response Rate – ORR) based on RECIST v1.1 and irRECIST, as well as the number and percentage of subjects meeting criteria of SD, PR, or CR over a period of at least 4 weeks (Overall Disease Control Rate – ODCR) will be displayed along with the corresponding 95% binomial CIs. In calculating ORR and ODCR, subjects who drop out prior to meeting the responder criteria will be considered as non-responders. Descriptive statistics will be presented for duration of response, defined as the time from the first response of PR or CR to

the date of disease progression or death. Tumor response and tumor marker CA-125 will be presented in subject listings.

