#### **3.1.2 Reporting of Numerical Values**

All clinical study data will be presented in subject data listings. All by-visit summarizations will be conducted using data from Cycle 1, Cycle 2, and/or the last cycle, as applicable. All data presentations will be by the planned cohorts in the protocol, separately for Phase 1 and Phase 2.

Descriptive statistics (n, mean, standard deviation, median, minimum and maximum) will be calculated by cohort for continuous variables.

Frequencies and percentages will be presented by cohort for categorical and ordinal variables. If there are missing values, the number missing will be presented, but without a percentage.

Means and medians will be reported to one decimal place more than the data reported in the EDC. Standard deviations will be reported to two decimal places more than the data reported. Minimum and maximum will be reported to the same number of decimal places captured in the EDC.

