#### **3.1.4 Handling of Missing/Incomplete Values**

Unless otherwise explicitly specified, missing data will not be imputed.

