### **3.8.3 Overall Survival**

Overall survival (OS) time will be based on data collected during study and Post Study Follow-up. OS time is defined as the time from the start date of the treatment (Day 1) to the date of death due to any cause and will be analyzed descriptively.

The number and percentage of subjects who died, who were lost to follow up, and who survived will be summarized. Subjects who withdrew from the study or were lost to follow-up (survival status unknown) will be censored at the date of last contact/last data point collected in the CRF.

OS Rate and the corresponding 95% confidence intervals at 6 months and 12 months will be calculated based on Kaplan-Meier product limit estimates and will be displayed along with the corresponding number of subjects at risk at each time point. OS time will be summarized descriptively. The 25th percentile, median, 75th percentile, corresponding 95% CIs as well as the minimum and maximum survival time will be calculated using the Kaplan-Meier method. In addition, OS estimates will be presented graphically.

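### Duration of response is summarised with ordinary descriptive statistics and no censoring rule, so taken as written ongoing responders have no value and the summary is biased short

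*SAP*

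**What the plan says.** **Duration of response.** SAP 3.8.2 gives it one sentence: "Descriptive statistics will be presented for duration of response, defined as the time from the first response of PR or CR to". It closes the interval at "the date of disease progression or death". It names no estimator and says nothing about a responder with neither event.

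**What descriptive statistics means here.** SAP 3.1.2: "Descriptive statistics (n, mean, standard deviation, median, minimum and maximum) will be calculated by cohort for continuous variables". None of these allows for censoring.

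**Missing values.** SAP 3.1.4: "Unless otherwise explicitly specified, missing data will not be imputed".

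**The other time-to-event variables.** For PFS, SAP 3.8.1 names the estimator ("where PFS time will be calculated using the Kaplan-Meier method") and a censoring rule ("Subjects without documentation of progression at the time of the analysis will be censored at the date of the last tumor response assessment", or at start of other therapy or last contact if earlier). For OS, SAP 3.8.3 also names Kaplan-Meier, and states that subjects who withdrew or were lost "will be censored at the date of last contact/last data point collected in the CRF". Both rules are written for their own variable only. The list of figures in SAP section 6 has Kaplan-Meier plots of PFS and OS and none of duration of response.

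**Protocol.** Sections 8.5.3.4 (RECIST 1.1) and 8.6.5 (irRECIST) run the duration from first response to documented recurrence or progression. Death is not an end point there, and neither section covers a response still ongoing at analysis.

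**The concern.** A duration that ends at progression or death is a time-to-event variable. For a responder with neither event, the SAP's definition yields no end date, and 3.1.4 gives no licence to supply one. The natural programming result is a missing value, so the summary covers completed responses only. Those are the shorter ones, because a long response is the likeliest to be unfinished at the cut-off.

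Unfinished responses are foreseeable. Protocol 3.1.12 lets MEDI4736 continue until confirmed progression for subjects who finish the core study with stable disease or better. Protocol 3.1.10 takes subjects off study when they start other anti-cancer therapy, withdraw or are lost. Protocol 3.1.16 ends outcome collection three years after treatment start.

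What is at stake is how durable responses to an immunotherapy combination appear in the study report. No hypothesis test is involved.

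**Working it through.** The documents give no figure for duration of response, so there is none to reproduce. The check asks which direction the error takes and how large it could be on the planned schedule.

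**Follow-up after first response.** Inputs: enrolment 24 months and study length 39 months (Protocol 3.1.15); outcome collection for 3 years from treatment start (Protocol 3.1.16); first on-treatment scan on Day 85, about 2.8 months (Protocol 3.2).
- Last subject enrolled: 39 − 24 = 15 months on study; 15 − 2.8 ≈ 12 months after a response first seen at that scan.
- Earliest subjects: capped at 36 months; 36 − 2.8 ≈ 33 months.

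**Assumptions, not in the documents.** Durations are exponential with true median m, and follow-up after response is uniform from a = 12 to b = 33 months.

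**Formulas.** With λ = ln 2 / m, the share still ongoing is q = [2^(−a/m) − 2^(−b/m)] / [λ(b − a)]. If ongoing responses are dropped, the median of the rest is t = −ln[(1 + q)/2] / λ, valid while t ≤ a.

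**Example, m = 6.** λ = 0.1155. q = (0.2500 − 0.0221) / (0.1155 × 21) = 0.2279 / 2.426 = 0.094. t = −ln(0.547) / 0.1155 = 0.6034 / 0.1155 = 5.2 months.

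A simulation of 400,000 responses per scenario agrees and supplies the means, in months:

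| True median | True mean | Share ongoing | Ongoing dropped: median / mean | Last assessment taken as end: median / mean | Kaplan-Meier median |
|---|---|---|---|---|---|
| 4 | 5.8 | 3% | 3.8 / 5.2 | 4.0 / 5.6 | 4.0 |
| 6 | 8.7 | 9% | 5.2 / 6.7 | 6.0 / 7.8 | 6.0 |
| 9 | 13.0 | 20% | 6.7 / 8.1 | 9.0 / 10.4 | 9.0 |
| 12 | 17.3 | 29% | 7.6 / 9.0 | 12.0 / 12.3 | 12.0 |

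**Reading the table.** Dropping ongoing responders shortens both median and mean in every row. Taking the last assessment as the end shortens the mean in every row but leaves the median alone, because no follow-up ends before the true median. Kaplan-Meier with censoring recovers the median throughout.

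**Sensitivity to follow-up.** With 6-30 months (later responses, some early withdrawal), the medians with ongoing responses dropped are 3.5, 4.7, 5.7 and 6.4 for the same true medians. With 3-12 months (an early data cut) they are 2.5, 2.8, 3.1 and 3.3, with 30% to 66% ongoing. Using the last assessment as the end can then shorten the median too: 7.9 for a true 9 at 6-30 months.

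**The case against.** **The SAP omits a rule; it does not adopt a wrong one.** A reader might infer that the plan excludes ongoing responders by design. It nowhere says so. Nor does a descriptive summary rule out Kaplan-Meier in this SAP: 3.8.3 says "OS time will be summarized descriptively" and then gives Kaplan-Meier quantiles, so a programmer could do likewise here. This stands as a limit on the claim but does not close the gap. For OS the estimator and censoring rule are written out; for duration of response the text stops, and 3.1.2 points to ordinary summaries.

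**The median need not be short under every handling.** A reader might infer that counting the last assessment as the end has the same effect as dropping the responder. It does not: on the planned schedule only the mean is short.

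**The effect may be modest.** With follow-up of only 3-15 months after response, a true median of 6 would appear as about 3.2, and a reader might conclude that the median is roughly halved. The documents' schedule does not support so short a follow-up as the base case; 12-33 months gives about 5.2.

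**Little depends on it.** Duration of response is not in the protocol's endpoint table, Protocol 4.1.1 or the efficacy variables of SAP 3.3.1. No table or figure title names it. Listings 16.2.11 and 16.2.13 should let a reader reconstruct individual durations. This stands, and it is why the point is minor.

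**A Kaplan-Meier median will be weak.** As an illustration only, the 15-20% response rate for second-line chemotherapy in Protocol 1.1, applied to 41 subjects, gives 41 × 0.15 ≈ 6 to 41 × 0.20 ≈ 8 responders. SAP 3.8.2 uses the ITT population, and 3.1.2 presents results by cohort and phase, so actual groups will differ. The imprecision is real and should be reported.

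**Conclusion.** The point holds as a minor one. Duration of response is the one time-to-event summary in SAP 3.8 without an estimator for censored data or a censoring rule, and the method named there cannot handle an ongoing response. Taken as written, the summary covers completed responses only and is biased short.

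The size for this trial cannot be derived, because the number of responders, their true durations and the withdrawal rate are not in the documents. On the assumed exponential model and planned schedule, the median falls short by about 0.2 months for a true median of 4 (4 − 3.8), 0.8 for 6, 2.3 for 9 and 4.4 for 12. Shorter follow-up enlarges this; complete follow-up of every responder to progression or death removes it.

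A reader might also infer that the trial's efficacy conclusion is compromised. It is not: the primary six-month PFS test, the response rates and OS do not use this quantity.

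**What to change.** In SAP 3.8.2:

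1. Estimate duration of response by Kaplan-Meier, applying the PFS censoring rule of SAP 3.8.1, including its handling of other therapy.
2. Report the median with its 95% CI, the number of ongoing (censored) responses, and each responder's duration marked as ended or ongoing.
3. Settle the end point. The SAP counts progression or death; Protocol 8.5.3.4 and 8.6.5 count progression or recurrence only. Choose one definition and say how a death without progression is treated.

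The cost is a few sentences of SAP text and one added table block or listing column. The data and software are those already planned for PFS. The drawback is that with few responders the Kaplan-Meier median will be imprecise or may not be reached, which is why the individual durations should be shown beside it.
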